### Figure 1: Study Flow Diagram

#### 5.1.1. End of Study Definition

The end of study definition for this study is the last visit of the last patient.

#### 5.2. Planned Interim Analysis

No interim analysis is planned.

### 6. SELECTION, WITHDRAWAL, AND REPLACEMENT OF PATIENTS

#### 6.1. Number of Patients Planned

Approximately 74 patients with a 2:1 randomization to alirocumab and placebo are planned.

##### 6.1.1. Rescreening of Patients

Patients who do not meet eligibility criteria during the initial screening may rescreen only once. Patients who are rescreened after the screening window ends must re-consent for study participation and repeat all screening procedures.

Patients who do not meet all eligibility criteria during the initial screening, and are still within the screening window, may retest those assessments that did not meet eligibility criteria once.

#### 6.2. Study Population

The study population will consist of male and female patients,  $\geq 18$  years of age diagnosed with HoFH, except patients known to have null/null mutations in both LDLR alleles.

##### 6.2.1. Inclusion Criteria

A patient must meet the following criteria to be eligible for inclusion in the study:

1. Males and females  $\geq 18$  years of age at the time of the screening visit.

2. Diagnosis of HoFH by at least 1 of the following genotype or clinical criteria (all patients on LDL apheresis must be diagnosed based on genotype):
  - a. Documented homozygous or compound heterozygous mutations in both LDLR alleles  
**Note:** Patients with known null mutations in both LDLR alleles are excluded (see Exclusion Criteria)
  - b. Presence of homozygous or compound heterozygous mutations in Apo B, PCSK9 or LDLRAP1
  - c. Presence of double heterozygous mutations, ie, mutations on different genes in the LDLR, Apo B or PCSK9 alleles
  - d. Untreated TC >500 mg/dL (12.93 mmol/L) and TG <300 mg/dL (3.39 mmol/L)

**AND**

Both parents with history of TC >250 mg/dL (6.46 mmol/L) **OR** cutaneous or tendinous xanthoma before age 10

3. Receiving a stable dose of a statin at the screening visit

**Note:** Patients who are not able to tolerate a statin or if statins were found to be ineffective may be included in the study but the reason should be documented in the case report form (CRF).

4. If undergoing LDL apheresis, must have initiated LDL apheresis at least 3 months prior to screening and must have been on a stable weekly (every 7 days) or every other week (every 14 days) schedule or stable settings for at least 8 weeks
5. Willing to maintain a stable low fat or heart-healthy diet for the duration of the study
6. Willing and able to comply with clinic visits and study related procedures
7. Provide signed informed consent

#### **6.2.2. Exclusion Criteria**

A patient who meets any of the following criteria will be excluded from the study:

1. Documented evidence of a null mutation in both LDLR alleles
2. Use of a PCSK9 inhibitor within 10 weeks from screening visit
3. Background medical LMT that has not been stable for at least 4 weeks (6 weeks for fibrates, 24 weeks for mipomersen, 12 weeks for maximum tolerated dose of lomitapide) before the screening visit

Patients will have the option to enter the optional run-in period. Once the patient is stable on his/her background medical LMT for the appropriate amount of time, the patient may enter the screening period.

4. LDL apheresis schedule/apheresis settings that have not been stable for at least 8 weeks before the screening visit or an apheresis schedule/settings that is not anticipated to be stable over the next 24 weeks

Patients will have the option to enter the optional run-in period. Once the patient is stable on his/her background lipid apheresis schedule/settings for the appropriate amount of time, the patient may enter the screening period.

5. Use of nutraceuticals or over-the-counter (OTC) therapies known to affect lipids, at a dose/amount that has not been stable for at least 4 weeks prior to the screening visit or between the screening and randomization visits.

Patients will have the option to enter the optional run-in period. Once the patient is stable on his/her nutraceuticals or OTC therapies for the appropriate amount of time, the patient may enter the screening period.

6. Presence of any clinically significant uncontrolled endocrine disease known to influence serum lipids or lipoproteins. This may include newly diagnosed (within 3 months prior to randomization visit [week 0/day 1]) diabetes mellitus, or signs and symptoms of hypothyroidism.

**Note:** Patients on thyroid replacement therapy can be included if the dosage of replacement therapy has been stable for at least 12 weeks prior to screening and the thyroid stimulating hormone (TSH) level is within the normal range at the screening visit

7. Unstable weight (variation >5 kg) within 2 months prior to the screening visit (week -2)
8. Initiation of a new diet or major change to a previous diet within 4 weeks prior to screening
9. Chronic use of systemic corticosteroids, unless on a stable regimen of 10 mg daily prednisone equivalent or less for at least 6 weeks prior to randomization

**Note:** topical, intra-articular, nasal, inhaled and ophthalmic steroid therapies are not considered as 'systemic' and are allowed

10. Use of estrogen or testosterone therapy unless the regimen has been stable in the past 6 weeks prior to the screening visit and there are no plans to change the regimen during the study
11. Systolic blood pressure >160 mmHg or diastolic blood pressure >100 mmHg at the screening visit (1 repeat measurement is allowed)
12. LDL-C level <70 mg/dL (1.81 mmol/L) at the screening visit
13. History of a MI, unstable angina leading to hospitalization, coronary artery bypass graft surgery, percutaneous coronary intervention, uncontrolled cardiac arrhythmia, carotid surgery or stenting, stroke, transient ischemic attack, valve replacement surgery, carotid revascularization, endovascular procedure or surgical intervention for peripheral vascular disease within 3 months prior to the screening visit
14. History of New York Heart Association (NYHA) class IV heart failure within 12 months before screening
15. History of cancer within the past 2 years, except for adequately treated basal cell skin cancer, squamous cell skin cancer, or in situ cervical cancer
16. Use of any active investigational drugs within 1 month or 5 half-lives prior to the screening visit, whichever is longer

17. Conditions/situations such as:

- Any clinically significant abnormality identified at the time of screening that, in the judgment of the investigator or any sub-investigator, would preclude safe completion of the study or constrain endpoints assessment; eg, major systemic diseases, patients with short life expectancy
- Considered by the investigator or any sub-investigator as inappropriate for this study for any reason, eg:
  - Deemed unable to meet specific protocol requirements, such as scheduled visits
  - Deemed unable to tolerate injections as per the patient or the investigator
  - Investigator or any sub-investigator, pharmacist, study coordinator, other study staff or relative thereof directly involved in the conduct of the protocol, etc.
  - Presence of any other conditions (eg, geographic or social), either actual or anticipated, that the investigator feels would restrict or limit the patient's participation for the duration of the study

18. Laboratory findings during screening period (not including randomization labs):

- Hepatitis B surface antigen and/or Hepatitis C antibody (associated with a positive HCV RNA polymerase chain reaction) at the screening visit
- Positive serum beta-human chorionic gonadotropin (hCG) or urine pregnancy test in women of childbearing potential
- Estimated glomerular filtration rate (eGFR)  $<30$  mL/min/1.73 m^2 (calculated by central lab)
- Alanine aminotransferase (ALT) or aspartate aminotransferase (AST)  $>3$  x upper limit of normal (ULN) (1 repeat lab is allowed)
- Unexplained serum creatine phosphokinase CPK  $>5$  x ULN (1 repeat lab is allowed)

19. Known hypersensitivity to monoclonal antibody therapeutics

20. Member of the clinical site study team and/or his/her immediate family

21. Pregnant or breastfeeding women

22. Women of childbearing potential\* who are unwilling to practice highly effective contraception prior to the initial dose/start of the first treatment and for the duration of the study. Highly effective contraceptive measures include stable use of combined (estrogen and progestogen containing) hormonal contraception (oral, intravaginal, transdermal) or progestogen-only hormonal contraception (oral, injectable, implantable) associated with inhibition of ovulation initiated 2 or more menstrual cycles prior to screening; intrauterine device (IUD); intrauterine hormone releasing system (IUS); bilateral tubal ligation; vasectomized partner; and or sexual abstinence\*\*.

\*Postmenopausal women must be amenorrheic for at least 12 months in order not to be considered of childbearing potential. Pregnancy testing and contraception are not required for women with documented hysterectomy or oophorectomy.

\*\*Sexual abstinence is considered a highly effective method only if defined as refraining from heterosexual intercourse during the entire period of risk associated with the study treatments.

### **6.3. Premature Withdrawal from the Study**

A patient has the right to withdraw from the study at any time, for any reason, and without repercussion.

The investigator and/or sponsor have the right to withdraw a patient from the study if it is no longer in the interest of the patient to continue in the study, or if the patient's continuation in the study places the scientific outcome of the study at risk (eg, if a patient does not or cannot follow study procedures). An excessive rate of withdrawals would render the study uninterpretable; therefore, unnecessary withdrawal of patients should be avoided. The site will be provided a retention manual outlining the best practices for patient retention.

Patients who are withdrawn prematurely from the study will be asked to complete study assessments, as described in Section [8.1.2](#).

The investigator should make the best effort to contact any patient (eg, contacting patient's family or private physician, reviewing available registries or health care database) who fails to return to the site and to determine health status, including vital status at a minimum. Attempts to contact such patients must be documented in the patient's records (eg, times and dates of attempted telephone contact, receipt for sending a registered letter).

Rules for discontinuation of study treatment (permanent or temporary) are discussed in Section [7.4.2](#).

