### 4.2. Primary and Secondary Endpoints

#### 4.2.1. Primary Endpoint

The primary efficacy endpoint is the percent change in LDL-C from baseline to week 12 in the ITT population for alirocumab 150 mg Q2W as compared with placebo in patients with HoFH.

The percent change in LDL-C from baseline to week 12 is defined as:

$$\frac{100 \times (\text{LDL-C value at week 12} - \text{LDL-C value at baseline})}{\text{LDL-C value at baseline}}$$

For LDL-C analysis, both calculated and measured LDL-C values will be taken into account. In case both calculated and measured LDL-C values are available for the same sampling time point, the measured LDL-C will be considered. The baseline LDL-C value will be the last LDL-C value obtained before the first dose of double-blind-study drug. For randomized but not-treated patients, baseline will be defined as the last value before randomization. The LDL-C at week 12 will be the LDL-C value obtained within the week 12 analysis window, regardless of adherence to treatment (ITT estimand).

All calculated and measured LDL-C values (scheduled or unscheduled, fasting or not fasting) may be used for the primary efficacy endpoint, if appropriate, according to the above definition. The analysis window used to allocate a time point to a measurement will be defined in the statistical analysis plan (SAP).

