### 7.4.2. Study Drug Discontinuation

Study drug should be continued whenever possible. In the event the investigational study drug dosing is stopped, it should be determined if the stop can be made temporarily; permanent discontinuation should be a last resort. In any case, the patient should remain in the study as long as possible.

Patients who permanently discontinue study drug during the double-blind treatment period should remain in the study and undergo all double-blind study visits and procedures with the exception of dosing with study drug. At the time of study drug discontinuation, the patient should have, as soon as possible, an unscheduled visit with assessments normally planned at end of double-blind treatment visit (this should take place within 5 days of discontinuation of study drug, if possible). Then, patients should resume the original study schedule until the end of the double-blind treatment period and all efforts should be made to perform the week 12 assessments at week 12. The original study schedule will continue until the end of the study visit (ie, follow-up phone call visit).

Patients who permanently discontinue study drug during the open-label period should have, as soon as possible, an unscheduled visit with assessments normally planned at the end of the open-label treatment period (this should take place within 5 days of discontinuation of the study drug, if possible). Upon completion of this visit, the original study schedule will resume until end of study (ie, follow-up phone visit).

Assessment of patients who do not consent to remain in the study after discontinuation of the investigational study drug should be managed according to Section [8.1.2](#).

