### 8.1.2. Early Termination Visit

If for any reason the patient refuses to continue the study, the patient should undergo an unscheduled visit as soon as possible with assessments normally planned at the end of double-blind treatment visit if the patient is in the double-blind treatment period (week 12 visit assessments); if the patient is in the open-label treatment visit, then the end of the open-label treatment assessments should be used (week 24 visit assessments). This visit should take place within 5 days of treatment discontinuation, if possible. The patient should be followed for at least 70 days from the last dose of study drug or up to recovery or stabilization of any AE to be followed-up as specified in this protocol, whichever comes last.

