### 5.6.1. Analysis of Primary Efficacy Variable

For the double-blind primary comparison of the alirocumab group to the placebo group, the percent change from baseline in LDL-C at week 12 will be analyzed in the ITT population using a mixed-effect model with repeated measures (MMRM) approach. All post-baseline data available within week 4 to week 12 analysis windows will be used and missing data are accounted for by the MMRM model. The model will include the fixed categorical effects of treatment group (alirocumab versus placebo), randomization strata (undergoing apheresis treatment [Yes vs. No] per IVRS/IWRS), time point (weeks 4, 8, and 12), treatment-by-time point interaction, and strata-by-time point interaction, as well as the continuous fixed covariates of baseline LDL-C value and baseline value-by-time point interaction.

This model will be run using Statistical Analysis Software (SAS) mixed procedure with an unstructured correlation matrix to model the within-patient errors. Parameters will be estimated using restricted maximum likelihood method with the Newton-Raphson algorithm. Denominator degrees of freedom will be estimated using Satterthwaite's approximation. This model will provide baseline adjusted least-squares means estimates at week 12 for both treatment groups with their corresponding standard errors.

Let  $\mu_0$  and  $\mu_1$  be the population means of the percent change from baseline in LDL-C at week 12 under placebo and alirocumab, respectively. The hypothesis that will be tested is " $H_0: \mu_0 = \mu_1$ " versus " $H_1: \mu_0 \neq \mu_1$ ". Therefore, the alirocumab treated group will be compared to the placebo group using an appropriate contrast statement tested at the 2-sided 0.05 level, with corresponding least squares estimate of mean difference, SE and 95% confidence interval.

Within treatment group least-square means and standard errors will be adjusted using weights equal to the observed proportion of patients in strata variable levels across the study population (i.e. "population weight"), rather than equal weights. Population weights are considered more appropriate than equal coefficients due to potential imbalances observed in the study population between levels of the randomization stratification factors.

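### Protocol 6.3 permits withdrawal from the study for not following procedures, which conflicts with a primary estimand that counts Week 12 LDL-C whatever the adherence

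*Protocol*

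**What the plan says.** - **Protocol 6.3** gives the investigator and sponsor two grounds for withdrawing a patient from the study: the patient's own interest, and a situation where continuing "places the scientific outcome of the study at risk (eg, if a patient does not or cannot follow study procedures". The same paragraph adds restraint: "An excessive rate of withdrawals would render the study uninterpretable; therefore, unnecessary withdrawal of patients should be avoided". It also promises sites a retention manual.
- **After withdrawal**, 6.3 says "Patients who are withdrawn prematurely from the study will be asked to complete study assessments, as described in Section" 8.1.2. That section asks for the Week 12 assessments if the patient leaves during the double-blind period, but on a different clock: "This visit should take place within 5 days of treatment discontinuation, if possible".
- **Protocol 4.2.1** defines the primary endpoint from the LDL-C value in the Week 12 window, "regardless of adherence to treatment (ITT estimand".
- **Protocol 7.4.2**, on stopping study drug, says "In any case, the patient should remain in the study as long as possible" and that "all efforts should be made to perform the week 12 assessments at week 12".
- **SAP 5.6.1** sets the primary analysis: "All post-baseline data available within week 4 to week 12 analysis windows will be used and missing data are accounted for by the MMRM model". SAP 5.6.1.2 acknowledges that this rests on missing at random. It prespecifies a pattern mixture sensitivity analysis, detailed in SAP 10.7.
- **SAP 10.2, Table 1a** assigns to Week 12 any sample from day 71 to day 98, or to the first open-label injection if that comes sooner.

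**The concern.** Under an estimand that ignores adherence, the patient who departs from the protocol is a patient whose Week 12 value must be counted. Section 7.4.2 follows that logic, and 6.3 allows the reverse: the departure can itself be the reason for ending follow-up. Under this estimand, ending follow-up does more harm to the scientific outcome than keeping the patient in.

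What is at stake is avoidable missing data that may be related to adherence, in a small trial. Patients who leave are not replaced (Protocol 6.4). Amendment 2 added the retention manual in order to limit missing data after early discontinuation of drug, so the ground in 6.3 also works against the sponsor's own aim.

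**Working it through.** **1. The plan's own figures.** The plan gives no figure for withdrawals of this kind. The inputs that set the scale are in Protocol 10.2: a 20-point difference, a re-estimated SD of 35, about 74 patients at 2:1, 5% non-evaluable, and 61% power.
- 74 × 2/3 = 49.3, so about 49 alirocumab and 25 placebo patients.
- 74 × 0.05 = 3.7, so about 4 non-evaluable and 70 evaluable.
- Two-sample t-test power at two-sided 0.05 is 60.0% with 47/23 and 60.9% with 46/24. The stated 61% is reproduced.

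**2. When a Week 12 value is lost.** The early termination visit is tied to stopping treatment and not to day 85. A patient who stops at day 43 and is withdrawn would have that visit by about day 48, which Table 1a assigns to Week 8. Nothing then falls in the Week 12 window. If the visit falls on days 71 to 98, before open-label dosing, it counts as Week 12, although a sample taken within 5 days of stopping may still show the drug's effect. Under 7.4.2 a later day-85 sample would supersede it, because SAP 6.5 selects the value nearest the target day. Under 6.3 no later sample follows.

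**3. Size if drug effect is lost.** Assume an on-drug effect of 20 points, and k of 49 alirocumab patients withdrawn, off drug and back at baseline by Week 12 (the return to baseline is the assumption in SAP 10.7), with only on-drug values before that.
- Effect regardless of adherence: 20 × (49 − k)/49.
- Effect the MMRM projects: about 20.
- Overstatement: 20 × k/49, which is 0.41 points per patient.
- As a share w of the arm, 20 × w: 0.4 at 2% (about 1 patient), 1.0 at 5% (2 to 3 patients), 2.0 at 10% (about 5 patients). All three rates are assumed.

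**4. Check by simulation.** Large-sample likelihood estimate with Weeks 4, 8 and 12, SD 35, on-drug effect of −20, and within-patient correlation 0.5 or 0.8. Positive values mean the effect is overstated.

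| Assumed situation | Bias in points (correlation 0.5 / 0.8) |
|---|---|
| 5% per arm withdrawn, alirocumab patients at baseline by Week 12, Week 8 still on-drug | 1.03 / 1.01 |
| Same, 10% per arm | 1.97 / 1.99 |
| 5% per arm, effect already lost at Week 8 | 0.68 / 0.56 |
| 5% per arm, breach raises LDL-C by 20 points in both arms | about 0 |
| Same breach, 2% on alirocumab and 8% on placebo | −1.20 / −1.17 |

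The last two rows represent breaches of background lipid therapy or apheresis, not of study drug.

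**5. Against the precision of the trial.** The standard error of the difference is about 35 × √(1/47 + 1/23) = 8.9 points. A bias of 1.0 point is 1.0/8.9 = 0.11 standard errors.

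**6. Reach of the pattern mixture model.** It imputes around the patient's own baseline for values missing after the last injection + 21 days. Last injection on day 57: 57 + 21 = 78, so day 85 is imputed around baseline. Last injection on day 71: 71 + 21 = 92, so day 85 is treated as missing at random.

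**The case against.** The strongest reply is that the plan already anticipates this. The pattern mixture model is prespecified for values missing after drug is stopped. On scheduled dosing it reaches patients whose last injection was on day 57 or before. A patient last injected on day 71 has had the final planned double-blind dose, so missing at random is a fair assumption for day 85. The clause in 6.3 is a permission, and its own paragraph discourages using it. Week 4 and Week 8 values stay in the model. Sites and the sponsor's operational team do not see lipid results after randomization (Protocol 7.6.1), so they cannot select patients on observed response. The biases computed here are small beside a standard error of 8.9 points. Finally, a patient who cannot attend will not supply a sample because a sentence has been deleted.

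Most of this stands, and it limits the point to a modest one. Three things remain. The pattern mixture model is a sensitivity analysis, so it leaves the primary estimate unchanged, and imputation does not replace an observation that could have been obtained. Blinding to lipids does not stop withdrawal from depending on adherence. The advice against unnecessary withdrawal does not settle the conflict, because the same paragraph names failure to follow procedures as an acceptable reason.

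**Conclusion.** The conflict between 6.3 and both 4.2.1 and 7.4.2 is real. Used early in the double-blind period, 6.3 can cost an obtainable Week 12 value, which the primary MMRM then handles as missing at random. If withdrawn alirocumab patients are off drug and back at baseline, the overstatement is about 0.4 points per patient (0.4, 1.0 and 2.0 points at assumed rates of 2%, 5% and 10% of the arm).

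A reader might go further and infer that the clause removes Week 12 values as a matter of course and biases the primary result toward alirocumab. The documents do not support that. A sample in the Week 12 window still counts, and no number of withdrawals is stated or implied. Study procedures also extend beyond dosing to visits, diet and stable background therapy. The direction therefore depends on who is withdrawn and why: the bias may be nil, or about 1.2 points against the drug if breaches of background therapy are commoner on placebo. Nor is the scenario left unaddressed, given the pattern mixture analysis. This is an inexpensive improvement to the protocol and does not invalidate the primary analysis.

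**What to change.** Amend Protocol 6.3 to agree with 4.2.1 and 7.4.2:
- State that non-adherence or failure to follow study procedures is, on its own, recorded as a protocol deviation and does not end follow-up.
- State that any patient withdrawn by the investigator or sponsor who still consents is asked for the Week 12 lipid sample at Week 12, in addition to the 8.1.2 visit.
- Keep the patient's right to withdraw and the patient-interest ground. The rules for stopping study drug are not affected.

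Protocol 15 requires an IRB/EC-approved amendment for a change in design, so a letter to sites alone is not enough; the retention manual can carry the same message. The cost is a short amendment, slightly less investigator and sponsor discretion, and some noisier Week 12 values from patients with poor adherence. It adds no visits beyond those already planned.
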